### 10.4 Assay Sensitivity

The analysis to show assay sensitivity will be also based on the concentration-QTc analysis of the effect on  $\Delta\Delta$ QTcF of 400 mg oral moxifloxacin using a similar model as for the primary analysis. That is, the relationship between moxifloxacin plasma concentration and  $\Delta$ QTcF will be investigated by linear mixed-effects modeling. The model will include  $\Delta$ QTcF as the dependent variable, moxifloxacin plasma concentration as the explanatory variable (0 for placebo), centered baseline QTcF (i.e., baseline QTcF for individual subject at each post-dose time point minus the population mean baseline QTcF for all subjects in the same treatment period) as an additional covariate, treatment (moxifloxacin=1 or placebo=0) and time (i.e., post-dose time point) as fixed effects, and a random intercept and slope per subject (Garnett et al). The geometric mean of the individual  $C_{max}$  values for subjects receiving the single dose of 400 mg moxifloxacin will be determined. The predicted effect and its 2-sided 90% CI for  $\Delta\Delta$ QTcF (i.e., slope estimate × concentration + treatment effect-specific intercept) at this geometric mean  $C_{max}$  will be obtained.

If the slope of the concentration-QTc ( $\Delta$ QTcF) for moxifloxacin is statistically significant at 10% level for 2-sided test and the lower bound of the 2-sided 90% CI of the predicted effect of  $\Delta\Delta$ QTcF is above 5 ms at the geometric mean Cmax for 400 mg moxifloxacin, assay sensitivity will be deemed to have been demonstrated.

### 10.5 By-Time Point Analysis

The by-time point analysis for QTcF will be based on a linear mixed-effects model with  $\Delta$ QTcF as the dependent variable, period, sequence, time (i.e., nominal post-dose time point), treatment (therapeutic dose of ITF2357, supratherapeutic dose of ITF2357, moxifloxacin, and placebo) and time-by-treatment interaction as fixed effects, and baseline QTcF as a covariate. An unstructured covariance matrix will be specified for the repeated measures at post-dose time points for subject within treatment period. If the model with an unstructured covariance matrix fails to converge, other covariance matrices such as compound symmetry and autoregressive will be considered. The model will also include a subject-specific random effect. If the fixed effects for period and/or sequence should prove to be not significant (i.e., if the P value > 0.1), these effects may be removed from the model and the analysis repeated without those covariates. From this analysis, the LS mean, SE, and 2-sided 90% CI will be calculated for the contrast "TTF2357 versus placebo" ( $\Delta\Delta$ QTcF) for each dose of ITF2357 at each post-dose time point, separately.

For HR, PR, and QRS interval, the analysis will be based on the change-from-baseline postdosing values ( $\Delta$ HR,  $\Delta$ PR, and  $\Delta$ QRS). The same (by-time point analysis) model will be used as described for QTcF. The LS mean, SE, and 2-sided 90% CI from the statistical modeling for both change-from-baseline and placebo-corrected change-from-baseline values will be listed in tables and graphically displayed.

The SAS code for the by-time point analysis for QTcF is as follows.

11-JUN-2021 (Final 2.0)

PROC MIXED DATA=ECG; CLASS SUBJID TREAT TIME PERIOD SEQUENCE; MODEL DQTc=BASE TREAT TIME TREAT\*TIME PERIOD SEQUENCE/DDFM=KR; random intercept / SUBJECT =SUBJID type=UN; REPEATED TIME / SUBJECT = PERIOD\*SUBJID type = un; LSMEANS TREAT\*TIME/CL DIFF ALPHA=0.1; RUN;

Where ECG = QT/QTc population, SUBJID = subject identifier, TREAT = treatment (therapeutic dose of ITF2357, supratherapeutic dose of ITF2357, moxifloxacin, and placebo), TIME = nominal post-dose time point, BASE = baseline QTcF, PERIOD = period, SEQUENCE = sequence, and DQTc =  $\Delta QTcF$ .

#### 10.6 Categorical Analysis

The analysis results for categorical outliers will be based on treatment-emergent events (i.e., new findings compared to baseline); T-wave morphology and presence of U-waves will be summarized in frequency tables with counts and percentages for both number of subjects and number of time points. Subject data will be summarized using the count of distinct subjects that fall into the category and the percentage of the total number of subjects. Time point data will be summarized using the count of the category and the percentage of the total number of subjects. Time point data will be summarized using the count of time points at which the assessments fall into the category and the percentage of the total number of subjects or number of time points at which assessments are performed. Counts (either number of subjects or number of time points) for each treatment group will be used as the denominator in the calculation of percentages unless otherwise specified.

A subject or time point will be determined as an outlier if the following criteria (which are assessed separately) are met for the ECG intervals (Table 2).

	eriterit for determining a subject or time point outlier
ECG	Categorical outlier criteria
interval	
QTcF	Treatment-emergent value of > 450 and $\leq$ 480 ms when not present at baseline (new onset)
	Treatment-emergent value of > 480 and $\leq$ 500 ms when not present at baseline (new onset)
Treatment-emergent value of $> 500$ ms when not present at baseline (ne	
	Increase of QTcF from baseline of $> 30$ and $\le 60$ ms
	Increase of QTcF from baseline > 60 ms
PR	Increase of PR from baseline $> 25\%$ resulting in PR $> 210$ ms
QRS	Increase of QRS from baseline > 25% resulting in QRS > 120 ms
HR	Decrease of HR from baseline >25% resulting in HR < 50 bpm
	Increase of HR from baseline >25% resulting in HR > 100 bpm

Table 2Criteria for determining a subject or time point outlier

All outliers will be summarized for each treatment group on the basis of incidence rates. A subject will be counted only once for a particular outlier event if the subject experiences more than 1 episode of that event. The total number of time points will be based on the number of observed time points across all subjects within a treatment group.

For T-wave morphology and U-wave presence, treatment-emergent changes will be assessed, i.e., changes not present at baseline. For each category of T-wave morphology and of U-waves, the category will be deemed as present if observed in any replicates at the time point.

The T-wave morphology and U-wave presence categories are described as follows (Table 3).

Category	Description
Normal T-wave (+)	Any positive T-wave not meeting any criterion below.
Flat T-wave	T-amplitude < 1 mm (either positive or negative), including flat isoelectric line.
Notched T-wave (+)	Presence of notch(es) of at least 0.05 mV amplitude on ascending or descending arm of the positive T-wave.
Biphasic	T-wave that contains a second component with an opposite phase that is at least 0.1 mV deep (both positive/negative and negative/positive and polyphasic T-waves included).
Normal T-wave (-)	T-amplitude that is negative, without biphasic T-wave or notches.
Notched T-wave (-)	Presence of notch(es) of at least 0.05 mV amplitude on descending or ascending arm of the negative T-wave.
U-waves	Presence of abnormal U-waves.

Table 3 T-wave morphology and U-wave presence categories (assessed manually)

### **10.7** Terminology and Definitions: Placebo-corrected $\Delta QTcF$ and Placebo-adjusted $\Delta QTcF (\Delta \Delta QTcF)$

Change-from-baseline QTcF ( $\Delta$ QTcF) will be used as the dependent variable in the concentration-QTc analysis and in the by-time point analysis.

# **By-time** point analysis

### Placebo-corrected $\Delta QTcF$ ( $\Delta \Delta QTcF$ )

In the by-time point analysis on the QTcF interval, LS mean, SE, and 2-sided 90% CI of  $\Delta OTcF$  and  $\Delta \Delta OTcF$  will be calculated for each active dose group and moxifloxacin group, as well as on placebo group for  $\triangle QTcF$  at each post-dose time point.

## Concentration-QTc analysis

### Placebo-corrected $\Delta QTcF$ ( $\Delta \Delta QTcF$ )

• In the concentration-QTc analysis, the term placebo-corrected  $\Delta QTcF$  ( $\Delta \Delta QTcF$ ) will be used for the model-predicted effect across concentrations on a population level.

Italfarmaco S.p.A.

 Definition: Model-predicted mean ΔQTcF in each active dose group minus modelpredicted mean ΔQTcF in the placebo group, which equals slope estimate × concentration + treatment effect-specific intercept.

#### Placebo-adjusted $\Delta QTcF$ ( $\Delta \Delta QTcF$ )

- In the concentration-QTc analysis, the term placebo-adjusted ΔQTcF (ΔΔQTcF) will be used to illustrate the underlying data on both subject and population levels.
- Definition for the estimated placebo-adjusted ΔQTcF on a subject level: observed ΔQTcF for each subject (on active dose group or moxifloxacin group or placebo group) minus the estimated time effect (i.e., the model-predicted mean ΔQTcF in the placebo group).
- Definition for the estimated placebo-adjusted ΔQTcF term on a population level: the average of individually estimated placebo-adjusted ΔQTcF values at the associated median plasma concentration within each concentration decile.

#### 10.8 Sample Size Considerations for Assay Sensitivity

#### 11. Pharmacokinetic Analyses

### 11.1 Handling of the Below the Lower Limit of Quantitation (BLQ) and the No Reportable Concentration Values

During PK and statistical analyses, drug concentrations BLQ of an assay will be considered as zero except when they occur between two non-BLQ concentrations where they will be considered as missing during PK calculations and estimations. A sample with a no reportable value occurring prior to the dosing for a given period will be replaced by zero. For tabulation, graphical representation and calculation purposes, all samples with no reportable value observed after dosing will be set to missing.

### 11.2 Handling of the Difference Between the Scheduled and the Actual Sampling Times

The actual clock time for dosing and the actual clock time for each collection time for the PK samples will be recorded using the electronic data capture. For all sampling times, the actual sampling times will be calculated as the difference between the sample collection actual clock time and the actual clock time of dosing. The actual post-dose sampling times expressed in hours and rounded off to three decimal digits will be used to calculate the PK parameters, except for pre-dose samples occurring prior to dosing, which will always be reported as zero (0.000), regardless of the time difference. In the PK section of the report, scheduled sampling times will be presented in concentration tables and mean graphs while actual times are presented for the individual graphs. A listing of the actual times for PKs will be provided for PK samples.

#### **11.3** Pharmacokinetic Parameters

### 11.3.1 Plasma Pharmacokinetic Parameters

For PK analysis of ITF2357 and its metabolites (ITF2374, ITF2375, ITF2440, ITF2563, ITF2955 glucuronide), and moxifloxacin for each period, a total of 19 blood samples will be collected from each subject at pre-dose (baseline) and 0.500, 1.00, 1.50, 2.00, 2.50, 3.00, 3.50, 4.00, 5.00, 6.00, 7.00, 8.00, 12.0, 24.0, 36.0, 48.0, 60.0, and 72.0 hours post-dose.

Only samples from subjects who receive ITF2357 and moxifloxacin will be analyzed, samples from subjects who receive placebo will be saved for analysis if needed.

ITF2357 will be quantified in all subjects administered with the study drug while the metabolites will be quantified only in a randomized group of 12 subjects, as no effect from the metabolites is expected on the QTc results. Before starting bioanalysis, the biostatistician will randomly select 12 evaluable subjects for plasma metabolite analysis. These will be the same 12 evaluable subjects randomely selected for urinary analysis. The samples that would not be analyzed will be kept frozen until bioanalysis results are obtained, if within these results any indication of a possible effect is found, all samples would be further studied using a similar analysis method.

Blood draws will be performed after the 15-minute supinely resting period around each time point for ECG extraction. The time tolerance window for blood samples collected during the confinement period will be  $\pm 10$  minutes for all samples. Sample collections done outside the pre-

defined time windows will not be considered as protocol deviations since actual post-dose sampling times will be used for pharmacokinetic and statistical analyses. A dead-volume intravenous catheter will be used for blood collection to avoid multiple skin punctures, when appropriate. Otherwise, blood samples will be collected by direct venipuncture.

Plasma concentrations for ITF2357 and its metabolites, and moxifloxacin will be used to calculate the following PK parameters by standard non compartmental methods:

AUC 0-t	Area under the concentration-time curve from time zero to the last measurable concentration, calculated using the trapezoidal method.
AUC 0-12	Area under the concentration-time curve from time zero to 12 hours, calculated using the trapezoidal method.
AUC 0-inf	Area under the concentration-time curve from time zero to infinity (extrapolated), calculated as $AUC_{0-t} + C_{last}/K_{el}$ , where $C_{last}$ is the last measurable concentration.
C max	Maximum observed plasma concentration.
Residual area	Residual area, calculated as 100*(1- AUC 0-t / AUC 0-inf ).
T max	Time of observed C max .
T  / 2 el	Elimination half-life, calculated as $ln(2)/K_{el}$ .
Kel	Elimination rate constant. This parameter will be the negative of the estimated slope of the linear regression of the ln-transformed concentration versus time profile in the terminal elimination phase. Best fit method will be used to calculate the K el from at least 3 concentration data points excluding the C max . Rsq adjusted, the goodness of fit statistic for the terminal elimination phase, adjusted for the number of points used in the estimation of Kel must be $\geq 0.8$ . If the Kel cannot be measured (e.g.: fewer than 3 non-zero concentrations in the terminal elimination phase or Rsq adjusted < 0.8), the PK parameters derived from K el will not be reported for that individual PK profile (AUC 0-inf , Residual area, and T  / 2 el). The timepoint where ln-linear K el calculation begins (K el Lower ) and the actual sampling time of the last measurable concentration used to estimate the K el (K el Upper ), as well as the Rsq adjusted for the ln-linear regression for the calculation of the elimination rate constant will be reported.
CL/F	Apparent total body clearance, calculated as Dose/AUC 0-inf .
V d /F	Apparent volume of distribution, calculated as Dose/Kel x AUC0-inf.

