12.1 Plasma PK Parameters

The following pharmacokinetic parameters will be calculated by standard non-compartmental methods for ITF2357 and metabolites: ITF2374, ITF2375, ITF2440, ITF2563 and ITF2955 glucuronide, and moxifloxacin in plasma:

- AUC_{0-t}: area under the concentration-time curve from time zero to the last measurable concentration
- AUC₀₋₁₂: area under the concentration-time curve from time zero to 12 hours
- AUC_{0-inf}: area under the concentration-time curve from time zero to infinity (extrapolated)
- C_{max}: maximum observed concentration
- Residual area: calculated as 100*(1- AUC_{0-t} / AUC_{0-inf})
- T_{max}: time of observed Cmax
- T_{½ el}: elimination half-life
- K_{el}: elimination rate constant
- CL/F: apparent total body clearance, calculated as Dose/AUC_{0-inf}
- Vd/F: apparent volume of distribution, calculated as Dose/K_{el} x AUC_{0-inf}

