12.2 Urine PK Parameters

The following PK parameters will be calculated for ITF2357 and metabolites ITF2374, ITF2375, ITF2440, ITF2563 and ITF2955 glucuronide ITF2955 in urine:

- Ae_{0-t}: Cumulative urinary excretion from time zero to time t, calculated as the sum of the amounts excreted over each collection interval. The amount excreted in urine for each time interval is calculated as the urine concentration multiplied by the urine volume.
- R_{max}: Maximum rate of urinary excretion, calculated by dividing the amount of drug excreted in each collection interval by the time over which it was collected
- T_{Rmax}: Time of R_{max}, calculated as the midpoint of the collection interval during which R_{max} occurred

Clr: Renal clearance, calculated as Ae_{0-t} / AUC_{0-t} (plasma)

Additional PK analysis may be performed. Upon Sponsor's request, pharmacokinetic repeats might be performed according to Syneos Health's SOP. If re-assays are requested for pharmacokinetic reasons, final results will include re-assay values, while results with original values will be presented in an appendix of the clinical study report as supportive data.

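### PK derivation rules need correcting: Vd/F is printed without brackets, CL/F and Vd/F are planned for undosed metabolites, and the urine end time in renal clearance is undefined

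*SAP*

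**What the plan says.** **Volume.** The plasma parameter table in SAP 11.3.1 gives Vd/F as "Apparent volume of distribution, calculated as Dose/Kel x AUC0-inf", with no brackets. Protocol 12.1 and the SAP list of abbreviations carry the same expression, and no section gives another form. The row above it in the SAP reads "Apparent total body clearance, calculated as Dose/AUC", with AUC taken from zero to infinity.

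**Analytes.** SAP 11.3.1 introduces the whole table with "Plasma concentrations for ITF2357 and its metabolites, and moxifloxacin will be used to calculate the following PK parameters". Protocol 12.1 opens its list with "The following pharmacokinetic parameters will be calculated by standard non-compartmental methods for ITF2357 and metabolites", then names the five metabolites and moxifloxacin. SAP section 5 lists CL/F and Vd/F as secondary parameters for all of these analytes. The treatments in SAP 3.3 are ITF2357, placebo and moxifloxacin; no metabolite is administered. Metabolites are to be measured in 12 randomly selected evaluable subjects.

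**Renal clearance.** Protocol 12.2 and SAP 11.3.2 define Clr as Ae0-t divided by plasma AUC0-t. Ae0-t is the total of the amounts recovered in the collection intervals, the last of which is 48 to 72 h; its end time is called only t. For plasma, AUC0-t stops at the last measurable concentration.

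**The concern.** SAP section 1 presents the document as the source of the algorithms for data derivation, so a programmer or a later reader is entitled to take a printed formula at face value. Three of these rules do not survive that.

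- The Vd/F expression, evaluated in the usual order, puts AUC in the numerator.
- For a metabolite, the only dose available is the parent's, so the result is not what its label says.
- The two terms of the renal clearance ratio share a subscript, but only the plasma one is defined, so they may cover different time spans.

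At stake are declared secondary endpoints. Characterising the pharmacokinetics of ITF2357 and its metabolites is a stated secondary objective.

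**Working it through.** The plan gives no figure to reproduce. The check is algebra and units, with illustrations where an input had to be assumed.

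**1. Vd/F**

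By definition Vd/F = (CL/F)/Kel. Inserting the plan's own CL/F = Dose/AUC gives Vd/F = Dose/(Kel × AUC).

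Units with brackets: mg ÷ (h⁻¹ × mg·h/L) = L. Units read left to right: (mg ÷ h⁻¹) × mg·h/L = mg²·h²/L. The latter rises with AUC where a volume should fall.

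Illustration for moxifloxacin: dose 400 mg and half-life 12 h (Protocol 5.2), so Kel = ln 2/12 = 0.0578 per h. AUC is assumed, because the documents give none.

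| AUC assumed (mg·h/L) | CL/F (L/h) | (CL/F)/Kel (L) | Dose/(Kel × AUC) (L) | (Dose/Kel) × AUC (mg²·h²/L) |
|---|---|---|---|---|
| 20 | 20.0 | 346.2 | 346.2 | 138,499 |
| 35 | 11.43 | 197.9 | 197.9 | 242,373 |
| 50 | 8.0 | 138.5 | 138.5 | 346,247 |

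The bracketed form agrees with CL/F exactly. The ratio of the last two columns is AUC² (400, 1,225, 2,500). It carries units and changes with the concentration unit chosen, so it shows that the expression is wrong but does not measure the size of an error.

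**2. Metabolites**

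Let F be the available fraction of the parent dose, fm the fraction of that converted to the metabolite, and CLm the metabolite's clearance. Then AUCm = F × fm × Dose/CLm, so Dose/AUCm = CLm/(F × fm).

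Compared with CLm/F, the value is too large by 1/fm. The documents do not give fm. For assumed values of 0.05, 0.1, 0.3 and 0.5 the factor is 20, 10, 3.3 and 2. Vd/F = Dose/(Kel × AUCm) inherits the same factor, so bracketing the formula does not cure this.

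Number affected: 12 subjects × 5 metabolites × 2 dose levels = 120 values of CL/F and 120 of Vd/F. This is a maximum, because a profile that fails the Kel rule (at least 3 points, adjusted r-squared of at least 0.8) yields neither.

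**3. Renal clearance**

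Assume constant renal clearance, mono-exponential decline with rate k, urine summed to 72 h and plasma AUC stopped at tlast. The computed Clr divided by the true one is then AUC0-72/AUC0-tlast = (1 − e^(−72k))/(1 − e^(−k·tlast)). For a 12 h half-life and tlast 24 h this is (1 − 2⁻⁶)/(1 − 2⁻²) = 0.9844/0.75 = 1.31.

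| Half-life assumed (h) | tlast 24 h | tlast 36 h | tlast 72 h |
|---|---|---|---|
| 4 | 1.02 | 1.00 | 1.00 |
| 6 | 1.07 | 1.02 | 1.00 |
| 9 | 1.18 | 1.06 | 1.00 |
| 12 | 1.31 | 1.13 | 1.00 |

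The documents give neither the half-life of ITF2357 nor its tlast, so this table is a range and not an estimate.

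**The case against.** **The missing brackets are a typing slip that will do no harm.** Both documents call for standard non-compartmental methods, SAP section 15 names Phoenix WinNonlin, and the CL/F row fixes the intended meaning. A reader might infer that the study report will contain wrong volumes. The documents do not support that; the software would probably return the right ones. What stands is that the written rule is wrong in three places and right in none. Text extraction is an unlikely cause, because the brackets in the residual-area formula survive in the same lists.

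**Metabolite values are not meaningless, and some may be dropped.** A reader might call them uninterpretable. They are a defined composite, CLm/(F × fm), so the fault lies in the label. SAP 11.3.2 does let the pharmacokineticist omit parameters, but only where concentration data are not amenable to evaluation. That does not take metabolite CL/F and Vd/F out of the planned outputs.

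**The renal clearance terms carry the same subscript.** This objection largely stands. A reader might infer that the plan mixes two time spans and that Clr is biased upward. Neither document says that urine t is 72 h or that it differs from plasma t. Inflation arises only if the last measurable concentration comes before the end of the urine collection that is summed.

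Nor can its size be read off the residual area as 1/(1 − residual). That is an upper bound, requiring urine collected to infinity. At a 20% residual it gives 1.25. With urine to 72 h and tlast 36 h, e^(−36k) = 0.20 and e^(−72k) = 0.04, so the factor is 0.96/0.80 = 1.20. With tlast 72 h it is 1.00.

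**Conclusion.** The derivation rules are wrong or incomplete as written, with consequences confined to descriptive secondary PK tables. The Vd/F expression is certainly wrong on a literal reading and probably harmless in execution. The planned metabolite CL/F and Vd/F are the more substantive fault: up to 120 values of each would be mislabelled, by a factor of 2 to 20 if fm lies between 0.5 and 0.05 (assumed). For renal clearance the established defect is an undefined end time. The possible inflation, 1.07 to 1.31 at tlast 24 h and half-lives of 6 to 12 h, rests on assumed values and on urine being summed to 72 h.

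A reader might extend this to the QT conclusion, but the documents do not support that. SAP 10.3.1 and 10.4 use plasma concentrations and geometric mean Cmax, and none of these three parameters enters. Protocol 12.4.2 plans no inferential PK analysis.

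**What to change.** - Write Vd/F = Dose/(Kel × AUC0-inf) in Protocol 12.1, SAP 11.3.1 and the SAP list of abbreviations.
- In Protocol 12.1, SAP section 5 and SAP 11.3.1, limit CL/F and Vd/F to ITF2357 and moxifloxacin. Alternatively, keep the metabolite values and label them as CLm/(F × fm) and the matching volume term. Metabolite-to-parent ratios are optional; they would be new parameters and are not needed to cure the fault.
- In Protocol 12.2 and SAP 11.3.2, define t for urine and use one common interval for Ae and AUC. This can be 0 to 72 h for both, with a stated rule for plasma below quantification, or both cut at the end of the same collection interval. Do not pair Ae0-72 with AUC0-inf: that creates a new mismatch in the downward direction (a factor of 1 − 2⁻⁶ = 0.98 at a 12 h half-life).

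The cost is wording only, with no new samples, assays or procedures.
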